9.3.9. Concomitant Medications/Therapies

Concomitant medications or therapies are defined as any nonstudy medications or therapies that were taken or given while the participant also received study treatment. A medication or therapy will be considered concomitant if the start date is on or after the date of the start of study treatment or if the start date is before the start of study treatment date and the end (stop) date is after the start of study treatment date. If the start date of a medication/therapy is partially or completely missing and the end (stop) date of the medication/therapy does not indicate that it ended prior to the start of study treatment, then the determination of the concomitant status will be based on the following:

- If the start year is after the year of the start of study treatment, then the medication/therapy is concomitant; else
- If the start year is the same as the year of the start of study treatment and
 - The start month is missing, then the medication/therapy is concomitant; else if
 - The start month is present and is the same or after the month of the start of study treatment, then the medication/therapy is concomitant; else
- If the start date is completely missing, then the medication/therapy is concomitant.

All other medications/therapies are considered prior medications/therapies.

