The renal component of the primary endpoint, improvement of  $\geq 30\%$  in eGFR, rather than complete recovery, is selected because renal repair after an insult is often maladaptive with inflammation, fibrosis, and vascular rarefaction leading to persistent cell and tissue malfunction and eventually chronic kidney disease (CKD). The frequency, severity, type, and duration of injury as well as the premorbid renal reserve seem to be risk factors for maladaptive repair (Venkatachalam, 2015). It is likely that maladaptive repair mechanisms will hinder complete recovery of renal function. In addition, patients with renal dysfunction are often continued on renal-protective medications, such as angiotensin-converting enzyme (ACE) inhibitors or angiotensin II receptor blockers (ARBs), which are known to reduce eGFR. Moreover, post-transplant patients are maintained on calcineurin inhibitors (CNIs), which are also known to reduce eGFR.

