7.2.4. Prior and Concomitant Medications/Procedures

Prior and concomitant medications (including vitamins and herbal preparations) and nonpharmacologic therapies and procedures will be summarized using the Safety Set. Prior medications or procedures are defined as medications or procedures taken within the 30 days prior to the first dose of study drug. Concomitant medications or procedures are defined as medications or procedures received by the participants on or after the first dose of study drug, including those started before the first dose of study drug and continued after the first dose of study drug.

Medications will be coded using the World Health Organization (WHO) Drug Dictionary version in use by Alexion at the time of the analysis, while nonpharmacologic therapies and procedures (any therapeutic intervention, such as surgery/biopsy or physical therapy) will be coded using MedDRA.

Medication summaries by treatment group (ie, number [%]) of participants using prior and concomitant medications will be presented by WHODrug Anatomical Therapeutic Chemical Level 3 and by WHO-Drug generic name. Procedures will be summarized similarly, but by MedDRA SOC and Preferred Term. Protocol-required vaccinations will be summarized similarly and will also be presented separately.

By-participant listings of these data will be provided separately.

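### SAP 9.3.9 has no branch for a partial start date known to precede treatment, so some medications continued into treatment are classed as prior

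*SAP*

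**What the plan says.** SAP 9.3.9 opens with a definition based on overlap: "Concomitant medications or therapies are defined as any nonstudy medications or therapies that were taken or given while the participant also received study treatment". For an earlier start it gives a date rule: the entry is concomitant "if the start date is before the start of study treatment date and the end (stop) date is after the start of study treatment date".

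Partial or missing start dates take a separate route. If the stop date "does not indicate that it ended prior to the start of study treatment, then the determination of the concomitant status will be based on the" branches listed there:

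1. "If the start year is after the year of the start of study treatment, then the medication/therapy is concomitant; else".
2. Same year as the start of treatment: concomitant if the month is missing, or if it is the same month or a later one.
3. "If the start date is completely missing, then the medication/therapy is concomitant".

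The section then closes with the default: "All other medications/therapies are considered prior medications/therapies".

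SAP 7.2.4 counts as concomitant anything received on or after the first dose, "including those started before the first dose of study drug and continued after the first dose of study drug". Protocol 8.5.2 says the same with Day 1 as the reference. SAP 7.2.4 also defines prior as taken within the 30 days before the first dose, and it plans medication summaries by treatment group as well as by-participant listings.

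**The concern.** Whether a medication is concomitant depends on overlap with treatment. The branches in 9.3.9 ask only when it started. They closely resemble the partial-date rule for adverse events in SAP 9.3.8, where onset is the right question. That suggests a drafting slip, though this is inference.

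The result runs the wrong way. A wholly unknown start date gives concomitant, while a start known to be earlier, with use known to continue, gives prior.

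At stake is the description of background care. Best supportive care is chosen by the investigator in both arms (Protocol 6.5). Protocol 4.2.1 notes that "post-transplant patients are maintained on calcineurin inhibitors (CNIs), which are also known to reduce eGFR", and says the same of ACE inhibitors and ARBs. Such drugs may well have been started long before the trial. Where their start dates are partial, the concomitant table by treatment group would omit them, to a degree that depends on how completely sites enter dates.

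**Working it through.** The plan gives no figure to reproduce. The check is to apply 9.3.9 literally to a set of date patterns and compare each result with the section's own overlap definition.

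**Inputs.** The branches and default of SAP 9.3.9; the definitions in SAP 9.3.9, SAP 7.2.4 and Protocol 8.5.2; an assumed start of treatment on 15 March 2022 (illustrative); an ongoing entry read as stopping after the start of treatment.

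| Start date as recorded | Stop date | Literal 9.3.9 | Definition |
|---|---|---|---|
| 10 May 2018 | ongoing, or 1 Sep 2022 | concomitant | concomitant |
| May 2018, day missing | ongoing, or 1 Sep 2022 | **prior** | concomitant |
| 2018 only | ongoing, or 1 Sep 2022 | **prior** | concomitant |
| Jan 2022, day missing | ongoing, or 1 Sep 2022 | **prior** | concomitant |
| Mar 2022, day missing | ongoing, or 1 Sep 2022 | concomitant | concomitant |
| 2022 only | ongoing, or 1 Sep 2022 | concomitant | concomitant |
| 2023 only | ongoing | concomitant | concomitant |
| Wholly missing | ongoing, or 1 Sep 2022 | concomitant | concomitant |
| 2018 only; May 2018; Jan 2022; 2022 only; wholly missing | 20 Jan 2022 | prior | prior |

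**Tracing one failure.** Start recorded as 2018 only, stop 1 September 2022. The stop date does not show an end before treatment, so the branches apply. 2018 is not after 2022, is not equal to 2022, and the date is not wholly missing. The default applies: prior. With the start recorded as 10 May 2018 and the same stop date, the general rule gives concomitant. That contrast needs no interpretation of ongoing entries.

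**Size.** The documents give no frequency of partial start dates, so the number of affected records cannot be calculated. For scale only: SAP section 4 reports 16 participants enrolled. If they split evenly, 16/2 = 8 per arm, and moving one user of a drug changes that arm's percentage by 1/8 = 12.5 points. With arms of 7 and 9 the step is 1/7 = 14.3 or 1/9 = 11.1 points. Because SAP 7.2.4 counts participants, the step occurs only if the participant has no other concomitant record in the same table row.

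**The case against.** The strongest reply is that a sensible programmer would let the opening definition govern. A 2018 start is known to precede treatment, so the general rule could be applied and the branches kept for starts that might fall on either side. The intent is clear from SAP 7.2.4 and Protocol 8.5.2. That is fair as to intent, but the text says status for partial dates is decided by the branches, and it closes with an explicit default. Two programmers could produce different tables from it.

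A second reply is that the contrast with full start dates is partly a matter of reading. For an ongoing drug the general rule asks for a stop date after the start of treatment, and there is none. Read strictly, the full-date ongoing drug would also be prior. This stands. The contrast is free of interpretation only when a later stop date is recorded, and the fix should settle ongoing entries for both routes.

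A third reply concerns consequence, and most of it stands. SAP 4.2 removes hypothesis testing and inferential treatment comparison. The listings in SAP 7.2.4 show every record, which in a 16-participant study is a direct view of background care. The rule is the same in both arms of a blinded trial, and no bias between arms is shown.

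A reader might also infer that a large share of chronic therapy, say 20% to 50%, would be missing from the table. The documents give no basis for such a range. Even if that share of start dates were partial, it would be an upper bound, because partial dates in the treatment month, or in the treatment year with no month, are handled correctly.

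**Conclusion.** The rule is wrong as written for one class of record: a partial start date whose known part precedes the start of treatment, on a medication not shown to have ended before treatment. On a literal reading the direction is certain: concomitant use is under-counted. The amount is unknown.

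The effect is confined to the descriptive prior and concomitant summaries on the Safety Set of a study that was terminated early. A reader might infer that the efficacy results are at risk, because some of these drugs lower eGFR and eGFR is part of Complete TMA Response. The documents do not support that. No endpoint is derived from this flag. The related intercurrent event in SAP 7.1.1 is initiation of disallowed therapy, and the affected records are by construction drugs begun before treatment. Neither responder status nor censoring can change.

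The point is worth correcting because the contradiction is plain, descriptive tables are what this SAP delivers, and the correction is nearly free.

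**What to change.** Add a branch to SAP 9.3.9 before the closing default, along these lines:

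*If the known part of a partial start date is before the start of study treatment, and the entry is ongoing, has no stop date, or has a stop date on or after the start of study treatment, the medication or therapy is concomitant. An ongoing entry counts as stopping after the start of study treatment, for full start dates as well.*

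The general rule for full dates asks for a stop strictly after the start of treatment. Using on or after in both places would avoid a new mismatch.

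The closing default should also be aligned with SAP 7.2.4. There, prior means taken within the 30 days before the first dose, so a drug continued across Day 1 meets both definitions. It would be a mistake to add that a drug is prior only if it stopped before the first dose, since that would contradict 7.2.4 and remove long-standing therapy from the prior table.

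The cost is a few lines of SAP text and a small change to the derivation, with no new data. The downside is that a few drugs that truly stopped before Day 1 but have no recorded stop date would be counted as concomitant. The rule already accepts this for wholly missing start dates.

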9.3.10. Serum Creatinine and eGFR

Serum creatinine measurements are not reliable with concurrent dialysis. Therefore, all serum creatinine values obtained while a participant is on dialysis will be excluded from all analyses. The eGFR rate will be imputed with a value of 10 (in mL/min/1.73 m²) while a participant is on dialysis. A participant will be considered on dialysis from the first day of dialysis through 5 days after the end of dialysis. A participant will be considered as not requiring dialysis at a specific post-Baseline time point if they have been dialysis free for at least 14 days prior to that time point. This rule will only be applied to postbaseline assessments of serum creatinine and eGFR.

The eGFR will be calculated based on creatinine using CKD-Epi equation in patients \geq 18 years of age:

eGFR = $141 \times \min(SCr/\kappa, 1)\alpha \times \max(SCr/\kappa, 1)-1.209 \times 0.993$ Age x 1.018 [if female] × 1.159 [if Black]

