7.7.3. Other Safety

7.7.3.1. Analyses for Laboratory Tests

Observed values and changes from Baseline in clinical chemistry, hematology, and urinalysis will be summarized descriptively by treatment group at Baseline and at each post-Baseline time point. For laboratory results that can be classified as normal, low, or high based on normal range values, shifts from baseline in classification will be summarized by treatment group for all study visits. For purposes of analyses, laboratory results based on standardized units will be used.

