9.3.11. Platelets and Hemoglobin

Platelet and hemoglobin measurements are not reliable with concurrent red blood cell (RBC) and/or platelet transfusions. Therefore, platelet values obtained on the day of a blood transfusion of platelets through 7 days after the transfusion will be excluded from all analyses. Hemoglobin values obtained on the day of a blood transfusion of either whole blood or packed RBCs through 7 days after the transfusion will be excluded from all analyses. This rule will only be applied to postbaseline assessments of platelets and hemoglobin.

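### The dialysis and transfusion exclusions in SAP 9.3.10 and 9.3.11 are written for all analyses, so they also leave the safety laboratory tables selectively incomplete

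*SAP*

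**What the plan says.** **Creatinine and eGFR (SAP 9.3.10).** The section calls creatinine unreliable during dialysis and rules that "all serum creatinine values obtained while a participant is on dialysis will be excluded from all analyses". The interval is wide: "A participant will be considered on dialysis from the first day of dialysis through 5 days after the end of dialysis". On-dialysis eGFR is not dropped: "The eGFR rate will be imputed with a value of 10" mL/min/1.73 m². The paragraph closes with its only carve-out: "This rule will only be applied to postbaseline assessments of serum creatinine and eGFR".

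**Hemoglobin and platelets (SAP 9.3.11).** The excluded hemoglobin results are "Hemoglobin values obtained on the day of a blood transfusion of either whole blood or packed RBCs through 7 days after the transfusion", again for all analyses. For platelets, "platelet values obtained on the day of a blood transfusion of platelets through 7 days after the transfusion will be excluded from all analyses". Baseline is exempt here too.

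**Safety laboratory tables (SAP 7.7.3.1).** Observed values and changes from baseline in chemistry and hematology are summarized by arm at each time point. For results that can be classed as low, normal or high, "shifts from baseline in classification will be summarized by treatment group for all study visits". The section does not mention 9.3.10 or 9.3.11. Laboratory change is a named safety endpoint in SAP 5.5.

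**Protocol.** Section 9.4.2.3 plans the same summaries and shifts and excludes nothing for dialysis or transfusion. SAP 4.2, which lists departures from the protocol's analyses, does not mention one.

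**The concern.** For efficacy the exclusions make sense: a creatinine lowered by dialysis, or a hemoglobin or platelet count raised by transfusion, should not count as a response. A safety table has a different job, which is to show what was measured in everyone treated.

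Participants are dialysed or transfused because they are doing badly. A rule triggered by those events removes laboratory results from the sicker participants at the times when they are sick. The by-arm tables then describe mainly the participants and visits that needed no support, and nothing in the plan tells the reader how many values were taken out. It would also be an undeclared departure from the protocol.

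**Working it through.** The plan states no figure to reproduce. The check has two parts: the scope of the text, and a count of scheduled values that fall inside each exclusion window.

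**1. Scope**

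- Both rules apply to all analyses. Each names one exemption, baseline, and neither names safety.
- SAP 7.7.3.1 adds no exemption of its own.
- Protocol 9.4.2.3 has no exclusion, and SAP 4.2 reports no change.

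The literal reading therefore reaches the safety tables.

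**2. Scheduled values**

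Protocol Table 1 schedules 12 post-baseline laboratory visits in the Treatment Period: Days 8, 15, 22, 29, 43, 57, 71, 85, 99, 127, 155 and 183. The counts below use nominal days. Dialysis and transfusion dates are assumed, because the documents give no frequencies.

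*Creatinine.* For dialysis from Day 1 to Day E, a visit on day v is excluded if v ≤ E + 5.

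| Dialysis ends | Excluded through | Values removed |
|---|---|---|
| Day 14 | Day 19 | 2 of 12 |
| Day 30 | Day 35 | 4 of 12 |
| Day 60 | Day 65 | 6 of 12 |
| Day 90 | Day 95 | 8 of 12 |
| Day 183 | whole period | 12 of 12 |

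*Hemoglobin.* For one red cell transfusion on day t, a visit is excluded if t ≤ v ≤ t + 7. That is 8 calendar days, while the early visits are 7 days apart.

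- Days 1 to 28: every transfusion day removes at least one scheduled value. It removes one on 25 of the 28 days and two on the other 3 (Days 8, 15 and 22).
- Days 29 to 98: a value is removed on 40 of 70 days (57%).
- Days 99 to 182: a value is removed on 24 of 84 days (29%).
- Four transfusions, on Days 3, 10, 17 and 24, remove all of Days 8, 15, 22 and 29.

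Platelets follow the same arithmetic after a platelet transfusion.

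**3. Which samples are lost**

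The hemoglobin window opens on the transfusion day itself, so a sample drawn that day before the transfusion is removed, although the transfusion cannot have altered it. A sample from the previous day is kept.

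The notes to Protocol Table 1 ask for visits on non-dialysis days where possible, and otherwise for study procedures before that day's dialysis. Creatinine collected under that instruction is removed all the same.

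The rule also splits single blood draws. In Protocol Table 9, blood urea nitrogen and potassium sit in the same panel as creatinine, and hematocrit and red cell count in the same panel as hemoglobin. Those results stay in the safety tables.

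**4. Weight of one participant**

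Sixteen participants were enrolled (SAP 4). At 1:1 that is about 16 / 2 = 8 per arm, so one participant missing at a visit is about 1 / 8 = 12.5% of an arm.

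**The case against.** **The events are still reported.** SAP 7.7 provides participant listings of all safety data, readable line by line with 16 participants. SAP 7.2.4 summarizes procedures by arm on the Safety Set, and Protocol 8.5.1 counts renal replacement therapy as a procedure. SAP 7.3.2 tabulates the proportion requiring dialysis over time, and on-dialysis eGFR is kept at 10. Clinically relevant laboratory changes can become adverse events, although Protocol 8.3.5 and 10.4.1 restrict this for findings tied to the underlying disease. This stands. A reader might infer that the worst renal and anemia values vanish from the safety results; the documents do not support that. The loss is confined to the summary and shift tables.

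**The removed values need not be the worst.** Dialysis lowers creatinine and transfusion raises hemoglobin. Peaks before the first dialysis day and nadirs before the transfusion day are kept, baseline is exempt, and under SAP 9.3.7 another value in the same visit window can fill the gap. This also stands, apart from the pre-transfusion and pre-dialysis samples described above.

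**The shift tables are coarse.** They use low, normal and high only. Entry requires hemoglobin at or below the lower limit of normal and acute kidney injury, so many participants probably start in the abnormal category and a deleted visit would seldom hide a new shift. This is fair for category changes. It does not cover the summaries of observed values and changes, or persistence of an abnormality across visits.

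**Keeping the values has its own bias.** Supported values can make mean changes look like improvement. This is correct, and it is why flags and counts belong in the fix. It also means one cannot say that the arm with more dialysis or transfusion would look safer under the present rule: the direction is unknown.

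**Little depends on it.** The trial stopped early and no hypothesis tests or inferential treatment comparisons are planned. That limits the consequence but does not resolve the conflict in the text.

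**Conclusion.** The point holds for the safety summary and shift tables. As written, SAP 9.3.10 and 9.3.11 remove post-baseline creatinine, hemoglobin and platelet values from tables that Protocol 9.4.2.3 plans without exclusions, and the removal is triggered by deterioration. In the illustrations it ranges from one scheduled hemoglobin value for most single early transfusions to all 12 creatinine values for a participant dialysed throughout.

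This rests on the literal scope of the rules, nominal visit days, assumed dialysis and transfusion dates, and no substitute value in the visit window.

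The total loss in this trial cannot be stated. A reader might multiply the protocol's literature figure of up to 40% or more on dialysis at presentation (Section 4.2.2) by 16 participants, 0.40 × 16 = 6.4, and conclude that about 6 people have no creatinine in the tables while on dialysis. That figure is not a rate observed here. It describes status at presentation, whereas the rule acts only after baseline, and it says nothing about how long dialysis lasts or who starts it later.

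**What to change.** - In SAP 9.3.10 and 9.3.11, platelets included, limit the exclusions to efficacy analyses.
- In SAP 7.7.3.1, state that safety summaries and shift tables use all observed values. Flag values obtained on dialysis (as 9.3.10 defines it) or within 7 days of the relevant transfusion, and report the number flagged per visit and arm.

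If the sponsor intends the exclusion to apply to safety, SAP 4.2 should declare it as a change from the protocol and the tables should show the number excluded per visit and arm.

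The cost is a few words, one flag and a count row; the data are already collected. The downside is small: mean changes in the safety tables will include treatment-modified values, and the flag and counts make that visible.

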### **3.2.3. Renal Response**

Renal Response is defined as an improvement in eGFR of  $\geq 30\%$  compared to baseline.

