#### Disease Characteristics

4. TMA within  $\leq$  14 days prior to Screening is associated with at least 1 of the following triggers:
  - a. Autoimmune (lupus nephritis, systemic sclerosis associated TMA [SSc-TMA])
  - b. Infection
  - c. Solid organ transplant (eg, kidney, pancreas, liver, heart, small bowel)
  - d. Drugs
  - e. Malignant hypertension

5. Confirmation of all of the following laboratory findings during the Screening Period and/or  $\leq 14$  days prior to the start of the Screening Period:
  - a. Platelet count  $< 150,000/\mu\text{L}$
  - b. Lactate dehydrogenase  $\geq 1.5 \times \text{ULN}$  and hemoglobin  $\leq \text{LLN}$  (based on age and sex)
  - c. Acute kidney injury as defined by meeting 1 or more of the following criteria (for kidney transplant recipients, the pre-TMA value is based on post-transplant eGFR):
    - Acute decline in eGFR  $\geq 50\%$  from pre-TMA value (pre-TMA value must be  $\leq 12$  months prior to Screening)
    - New acute kidney injury with an eGFR  $\leq 30 \text{ mL/min}/1.73 \text{ m}^2$
    - New initiation of dialysis due to TMA requiring  $> 1$  session and for no more than 14 days prior to Screening

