4.3. Changes from Analyses Specified in the Previous Version of the SAP

Abbreviations: FACIT = Functional Assessment of Chronic Illness Therapy; PA2 = Protocol Amendment 2; SAP = statistical analysis plan; TMA = thrombotic microangiopathy

5. **DEFINITIONS**

5.1. **Primary Endpoint**

The primary efficacy endpoint of the study is complete TMA response during the 26-week randomized Treatment Period.

Complete TMA response is defined as normalization of hematologic parameters (platelet count and LDH) and \geq 30% improvement in estimated glomerular filtration rate (eGFR) from Baseline (Table 2).

Table 2:	Overview of Complete Thromb	ootic Microangiopathy Response
----------	------------------------------------	--------------------------------

		TMA Response Parameter
Complete TMA response	Hematologic response	 Normalization of platelet count (defined as platelet count ≥ 150000/µL) without transfusion support during the prior 7 days Normalization of LDH (defined as LDH
		\leq 1.5 × upper limit of normal)
	Renal response	• Improvement in eGFR of ≥ 30% compared to Baseline

Abbreviations: eGFR = estimated glomerular filtration rate; LDH = lactate dehydrogenase; TMA = thrombotic microangiopathy

If a participant is not on dialysis at Baseline, baseline eGFR will be defined as the last nonmissing assessment value prior to the start of study treatment. If a participant is on dialysis at Day 1, baseline eGFR will be set to 10 mL/min/1.73 m². If a participant is on dialysis during the entire 26-week randomized Treatment Period or through early discontinuation of study drug, then the change in eGFR will not be calculated.

For complete TMA response, participants must have met all 3 TMA response parameters simultaneously, with each component meeting the requirement at 2 separate assessments obtained at least 24 hours apart, and any measurement in between. The first laboratory value will be assessed based on central laboratory results; the second laboratory value will be assessed based on the earliest value obtained \geq 24 hours after the first value and may be based on central or local laboratory results.

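### Because on-dialysis eGFR is imputed as 10, a participant with baseline eGFR at or below 7.69 who starts dialysis after Day 1 is scored as a renal responder, unless the SAP 5.1 exception applies

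*SAP*

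**What the plan says.** Four rules combine.

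- **Post-baseline eGFR on dialysis.** SAP 9.3.10 drops creatinine values obtained on dialysis as unreliable and replaces the eGFR: "The eGFR rate will be imputed with a value of 10". The window is wider than the dialysis days: "A participant will be considered on dialysis from the first day of dialysis through 5 days after the end of dialysis". The section limits this to post-baseline assessments.
- **Baseline eGFR.** SAP 5.1 has two cases. "If a participant is not on dialysis at Baseline, baseline eGFR will be defined as the last nonmissing assessment value" before study treatment, with no floor. "If a participant is on dialysis at Day 1, baseline eGFR will be set to 10" covers the other case.
- **Renal response.** In Protocol 3.2.3, "Renal Response is defined as an improvement in eGFR of" at least 30% over baseline. SAP 5.1 Table 2 uses the same criterion. Neither mentions dialysis.
- **Exception.** SAP 5.1 does not calculate a change in eGFR for a participant who is "on dialysis during the entire 26-week randomized Treatment Period or through early discontinuation of study drug".

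Entry criteria cap eGFR from above only: one kidney-injury criterion in Protocol 5.1 begins "New acute kidney injury with an eGFR" and sets a ceiling of 30. Protocol 6.5 lists dialysis as best supportive care. Starting it is therefore not one of the events that make a participant a nonresponder under SAP 7.1.1, which are stopping study treatment and starting a disallowed therapy.

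**The concern.** The value 10 stands in for very poor kidney function. It works as intended when the baseline is above 10, because a dialysis start is then scored as a decline. When the observed baseline is below 10, the same placeholder scores a dialysis start as an improvement, and far enough below 10 it reaches the response threshold.

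The SAP guards against the parallel problem for platelets. Normalization must be free of recent transfusion support, and SAP 9.3.11 removes post-baseline platelet values affected by transfusion. The renal criterion has no such condition.

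At stake is whether the renal tables can record the start of dialysis as renal benefit and so contradict the dialysis table for the same participant.

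**Working it through.** The plan states no cut-off for this situation; it follows from the plan's own 10 and 30%.

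**1. Cut-off.** With baseline B and an imputed value of 10, the percent change is (10 − B)/B. Response needs (10 − B)/B ≥ 0.30, so B ≤ 10/1.3 = 7.69.

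| Baseline eGFR | Change | Percent change | Renal criterion |
|---|---|---|---|
| 6 | +4 | 4/6 = +66.7% | met |
| 7 | +3 | 3/7 = +42.9% | met |
| 7.69 | +2.31 | 2.31/7.69 = +30.0% | met |
| 8 | +2 | 2/8 = +25.0% | not met |
| 10 (set, on dialysis at Day 1) | 0 | 0% | not met |

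Any off-dialysis baseline below 10 gives a positive change. The last row shows the inconsistency: a participant on dialysis since Day 1 scores 0% while still on it, and a new starter with baseline 7 scores +42.9% with the same dialysis status.

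**2. Short course.** Baseline 7, dialysis from Day 4 to Day 10. The on-dialysis window runs from Day 4 to Day 10 + 5 = Day 15. The scheduled laboratory visits on Days 8 and 15 both fall inside it and both score +42.9%. They are 7 days apart, so a 24-hour confirmation rule would be satisfied. The first renal response is dated Day 8.

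**3. Long course.** Protocol Table 1 has 12 post-baseline laboratory visits: Days 8, 15, 22, 29, 43, 57, 71, 85, 99, 127, 155 and 183. With baseline 7 and dialysis from Day 5 through Day 183, all 12 of 12 score as renal response, while the participant is also counted as on dialysis at Week 26. Dialysis did not cover the whole Treatment Period, so the exception does not literally apply.

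**4. Which endpoints move.**

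- *Directly:* renal response by visit, time to renal response, change in eGFR.
- *Response in at least one TMA parameter:* only at visits where neither the platelet nor the LDH criterion is met.
- *Complete TMA Response:* only if platelets and LDH are normalized at the same time and an imputed 10 is accepted under the rule "The first laboratory value will be assessed based on central laboratory results".
- *Loss of TMA Response:* masked only if platelets and LDH also stay normal.

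**5. Size of one case.** Arm sizes are not given. Assume 8 per arm (16/2), with a range of 6 to 10.

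- Response rate: 1/8 = 12.5 points (1/6 = 16.7; 1/10 = 10.0). For example, 2/8 = 25.0% (Clopper-Pearson 95% CI 3.2 to 65.1) becomes 3/8 = 37.5% (8.5 to 75.5).
- Mean change in eGFR: going from 7 to 10 adds 3/8 = 0.375, about 0.4 mL/min/1.73 m², compared with scoring no change (3/6 = 0.5; 3/10 = 0.3).

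**The case against.** The best counter-reading is that an on-dialysis visit has no qualifying value at all. Protocol 8.2.1 bases renal response on laboratory assessments, with eGFR calculated from serum creatinine. SAP 9.3.10 excludes on-dialysis creatinine from every analysis, and SAP 7.1.1 treats a missing binary value as nonresponse. This fails for renal response because SAP 9.3.10 supplies an eGFR for exactly these visits: the value is imputed, not missing, and nothing bars it from the response criterion. The argument has more force for Complete TMA Response and Loss of TMA Response, where the first value must come from the central laboratory. Those endpoints are therefore listed as conditional.

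Three further points stand. The second limb of the SAP 5.1 exception could be read to cover a new starter who then stops study drug, which narrows the group. The imputation usually works against response, since a new starter with a baseline above 10 is scored as declining. And dialysis at Week 26 and dialysis over time are reported separately, so the dialysis start would remain visible.

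A reader might infer that the primary endpoint is inflated, or that a treatment comparison or type I error is compromised. The documents do not support either. Complete TMA Response needs both hematologic criteria and acceptance of an imputed value, and SAP 4.2 removes hypothesis testing and inferential treatment comparisons. Nor do the documents suggest that the effect would favor one arm.

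**Conclusion.** The gap is real but narrow, and minor. As written, the rules score a dialysis start as renal response for a participant who is off dialysis at Day 1, has an observed baseline at or below 7.69, starts dialysis afterwards and falls outside the SAP 5.1 exception. Such a starter with a baseline between 7.69 and 10 is not a responder but shows a positive eGFR change.

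It would be too strong to say that any new dialysis start counts as response, or that response in at least one TMA parameter is always affected. The first needs a baseline at or below the cut-off; the second needs both hematologic criteria to be unmet at that visit.

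How many participants qualify is not in the documents and may be none of the 16. The effect is confined to descriptive rates, confidence intervals, means and Kaplan-Meier curves. The per-case sizes rest on the assumed arm sizes, and the 2/8 starting count is illustrative.

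**What to change.** In SAP 5.1 and 9.3.10, state that a post-baseline assessment inside the SAP 9.3.10 on-dialysis window:

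- does not meet the renal response criterion;
- cannot serve as a first or second qualifying value;
- counts as not meeting the renal component for Loss of TMA Response.

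For change in eGFR, keep the imputed 10, and add a summary that leaves out on-dialysis values for participants whose baseline is below 10. The main summary will still contain the positive changes, but the second one shows how much they matter.

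The cost is one or two SAP sentences and a small programming change, with no new data. The downside is possibly slightly fewer renal responders and slightly more recorded losses of response. SAP 4.1 describes the final analysis as still to come, so the rule can be fixed in advance instead of case by case.
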